Based on published studies(11-14), we have assumed a 6-month change in NAE/Cr within groups of 16.5 mEq/g. Assuming a conservative 12.5% loss-to-follow-up at 6 months (35 participants/group), we will have 80% power to detect a difference between groups in NAE/Cr as small as 11.4 mEq/g with a two-sided, Type I error rate of 0.05. Considering that expected change in NEA/Cr will be about 20-30 meq/d(11, 12, 14), we should be able to detect clinically important changes in NEA/Cr from the proposed intervention. For Aim#2, we are interested in estimating recruitment yields, compliance and other parameters that will inform the feasibility of a full-scale trial. With up to 83 participants recruited, we will be able to estimate the two-sided, 95% Clopper-Pearson Exact confidence interval with a width of 0.043 if the recruitment yield is 10%, and a width of 0.14 if the recruitment yield is 40%. For correlational analyses, 83 participants will allow us to detect correlation coefficients of 0.31 or larger with at least 80% power assuming a 2-sided 0.05 □.

Interventions and Interactions

Patients will be screened over the phone and in the clinic to see if they meet qualifications for the study. Once screened, they will be randomized into one of two groups- taking an oral bicarbonate supplement or a placebo.

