prot=g of protein consumed per day and pot=meqs of potassium consumed per day(19). The Short Physical Performance Battery (SPPB) is a well-characterized global measure of lower-extremity function and mobility. It will be assessed during screening (20, 21), at 3 and 6 months. The test consists of gait speed, chair stands, and balance; it is a strong predictor of disability and mortality in initially non-disabled older persons. SPPB scores of 4-9 have already been successfully used as a range associated with risk for developing mobility disability(21). The 400-meter walk is a measure of aerobic endurance where participants are instructed to complete the 400m distance (on a flat indoor surface) at their normal pace and the time to complete the walk is recorded in minutes and seconds. A comprehensive metabolic profile (CMP), including tCO₂, electrolytes, blood glucose and creatinine will be assessed at baseline and at 6-month follow-up. In conjunction with data from urine collections and analysis, CMP will allow calculation of fractional excretion of Na⁺, K⁺, Cl⁻, and the anion gap(22).

Bone Health. Because the kidney's capacity to excrete acid declines with age, acid-producing diets lead to a positive balance of protons and mild (often) subclinical acidosis. This acidic milieu facilitates release of Ca²⁺ from bone and increases bone turnover; it impairs osteoblast function and activates osteoclasts through stimulation of the proton-sensing receptor OGR1 and release of prostaglandin E2. Phosphate and bicarbonate released from bone mineral neutralize acid by a physicochemical reaction, leading to further Ca²⁺ release from the bone. In addition, renal Ca²⁺ excretion increases, through suppression of Ca²⁺ transporters and the calcium-sensing receptor (CaSR), which is exquisitely pH sensitive. CaSR regulates both renal Ca²⁺ absorption and parathyroid hormone release. Since a dietary acid load does not alter intestinal Ca²⁺ absorption, negative Ca²⁺ balance persists as long as the proton balance remains positive (33-73). This pathophysiologic mechanism explains why it is of great interest that we evaluate bone density in our study, which is testing the feasibility of neutralizing diet-dependent acid load in the elderly.

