collection of these data throughout the study. The first recall will be conducted at the SV to review all procedures and tools to be used. A “Food Amounts” booklet containing 2-D visual portions will be provided to the participant for use in standardizing portion sizes. Subsequent recalls will be conducted by telephone with trained interviewers from the CRU placing unscheduled telephone calls to participants at seven additional timepoints. When contacted by the staff, subjects will be asked to recall and report their dietary intake from the previous day’s 24-hour period. In addition to the first in-person SV recall, telephone recalls will be done within one week of the SV (1) to further assess eligibility (an average of both protein intake and K+ will be used to calculate the NEAP score), and within a 1-week period of each follow-up visit for a total of eight recalls during the study. Recalls will be randomly scheduled and will reflect both weekday and weekend intakes.

At the baseline visit and remaining in-clinic follow up visits, participants will spend approximately 4hr in the Clinical Research Unit (CRU), have their physical ability tested (FV2 and FV3 only), have blood drawn for blood gas analysis as well as blood for cystatin c and blood for storage. The blood gas draw will be performed in the CRU. Urine will be collected over the 4hr period (this is necessary because urine collections need to be monitored and refrigerated). Participants will be encouraged to take 500 ml of water during their stay at the CRU, to stimulate urine production. During these visits (not at FV2) the participants will also provide information about their dietary habits using the VioFFQ™ (Viocare, Inc., Princeton, NJ), which is a validated, web-format system for collecting food frequency data on a subject’s dietary behavior and food use patterns. The questionnaire will be self-administered. Participants will also receive a DXA scan of their hip at BV and FV3.

Table showing Study Schedule of events	SV	BV	FV1	FV2	FV3
Location of Visit	CRU	CRU	Phone Call	CRU	CRU
Study Week Number Activity/Assessment	-1 wk	0	1 mo	3 mo	6 mo
Informed Consent	X				
Cognitive Screen (MoCA)	X				
Fasting blood draw (CMP)	X			X	X
Urinalysis (Spot Urine)	X				X
SPPB	X			X	X
400m walk test		X		X	X
VITALS	X	X		X	X
DXA		X			X
24-hour Diet Recall to calculate NEAP	X		X	X	X
Medical History and Medications	X		X	X	X
Food Frequency		X			X
Blood Gas, Cystatin C, blood for storage		X			X

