Aim 1 Determine the feasibility of achieving ~50% reduction in net acid excretion (NAE/Cr meq/g) by the kidney after 6-months of oral bicarbonate supplementation vs. placebo. (NAE/Cr was measured at each visit.)

We will use mixed effects analysis of covariance (ANCOVA) to estimate change in NAE/Cr within randomized groups, including the baseline value of NAE/Cr and the intervention effect in the model. A contrast will be used to obtain estimates and 95% confidence intervals after 6-months. This approach utilizes all measurements obtained during follow-up and can provide unbiased estimates, if missing outcomes are related to outcomes obtained at other time points.

Aim 2 Ascertain recruitment yields, adherence to the intervention, adherence to the assessments, and sustainability of the intervention over 6 months; and collect data on variability and longitudinal correlations in kidney function, lean body mass, and functional outcomes to design a future full-scale clinical trial.

For recruitment yields, we will calculate the proportion of screened participants randomized, overall, and within gender and ethnic subgroups.

Adherence to the intervention will be measured as the proportion of the prescribed dose (bicarbonate or placebo) taken, based on pill counts.

Compliance with assessments will be determined by calculating proportion lost to follow-up at each visit and the percent of missing measurements.

Sustainability of the intervention will be assessed via: a) generalized estimating equations for repeated measures on the proportion of expected pills a participant took.

Means (proportions), variances, and 95% confidence intervals (exact CI where needed) will be calculated within intervention groups and for the difference between groups for all endpoints.

Correlations coefficients (both Pearson and Spearman) will be used to investigate the association between net endogenous acid production (NEAP) and other measures of interest, as well as changes in net acid excretion

(NAE) and measures of interest. (Measures of interest: tCO₂, blood bicarbonate (blood gas), eGFR, urineACR, SPPB, 400m walk, bone density).

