Power analysis: Based on published studies, we have assumed a 6-month change in NAE/Cr of 16.5 mEq/g within groups. Assuming a conservative 12.5% loss-to-follow-up at 6 months (35 participants/group remaining), we will have 80% power to detect a difference between groups in NAE/Cr as small as 11.4 mEq/g with a two-sided Type I error rate of 0.05. Considering that expected change in NEA/Cr will be about 20-30 meq/d we should be able to detect clinically important changes in NEA/Cr from the proposed intervention. For correlational analyses, 80 participants will allow us to detect correlation coefficients of 0.31 or larger with at least 80% power assuming a 2-sided 0.05 □.

Other Exploratory/Sensitivity Analyses:

Do NEAP and NAE correlate at baseline, when controlled for kidney function and caloric intake?

Do NAE and calcium excretion correlate at baseline and other time points, when controlled for kidney function and calcium intake?

Do NAE and sodium intake correlate? Do NAE and sodium excretion in the urine correlate? (An important one, if so, we will need to treat sodium intake as a confounder. There is physiological feasibility that these two may correlate.)

Does NEAP calculated from food recalls correlate with NEAP calculated from FFQs?

Human Subjects Protection

Human Subjects Involvement and Characteristics

We plan to recruit and randomize up to 83 older men and women who meet the inclusion/exclusion criteria described above. Participants will be randomized to bicarbonate capsules or placebo for 6 months. All assessments will be conducted during following visits and phone calls: screening phone call, 1 screening visit (SV1); 1 baseline visit (BV1); 1-month phone call, 3-months mid-intervention follow-up visit (FV1); and 1 post-intervention follow-up visit at 6-month (FV2).

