The nature, purpose, and risks of all procedures and protocols will be explained to each participant prior to obtaining the written consent. All examiners are trained in the standardized conduct of all assessments before data collection. Participants will be instructed to wear appropriate and comfortable clothing and standardized written instructions will be provided prior to each study visit. The primary outcome of interest (change in net acid excretion (NAE) by the kidney) was selected as an indicator of feasibility of implementing this intervention in elderly individuals. Oral bicarbonate will titrate dietary acid load, decrease net endogenous acid production (NEAP) and this will result in decreased acid excretion by the kidney. This dose (0.3mg/kg) was selected according to published studies, which indicated that it is generally safe and can decrease NEA ~ 50%(14). We have extensive experience measuring all of these outcomes in our research studies and the fact that there is such an easy-to-assess and inexpensive (simple chemical titration of titratable acid and ammonium) outcome to measure is an important advantage of our approach. Importantly, decreased NEA will also serve as quantitative measure of compliance.

Sources of Research Material

Participants will self-report personal information on paper survey forms including personal demographic data, race, health information, and psychological and social data. Results will also be recorded in a computer database. Data from the paper forms will be entered into an electronic database on a computer workstation. All material and data will be obtained solely for research purposes.

Potential Risks

The potential risks to study participants receiving bicarbonate supplementation have recently been reviewed by [name] who is a consultant on this study (7). In summary, the potential risks of this study include:

- 1) **Blood Draw.** Participants may experience temporary pain, bruising, bleeding and a small risk of infection or fainting or dizziness during the blood sample collection process. Only trained staff will be responsible for the collection of blood samples.

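### The stated 80% power at r = 0.31 fits baseline correlations but not correlations of 6-month change in NAE (about 75%), and those change correlations carry no arm term.

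*Combined protocol and SAP*

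**What the plan says.** The Analytical Plan, Aim 2, plans Pearson and Spearman coefficients for NEAP "and other measures of interest, as well as changes in net acid excretion" against tCO₂, blood bicarbonate, eGFR, urine ACR, SPPB, 400 m walk and bone density. It does not say whether arms are pooled, separated or adjusted for. The sentence just before it does refer to results within and between groups, but it covers means, proportions, variances and intervals, not correlations.

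Power for correlations is given twice. The Sample Size section says: "For correlational analyses, 83 participants will allow us to detect correlation coefficients of 0.31 or larger with at least 80% power". The power paragraph of the Analytical Plan says: "For correlational analyses, 80 participants will allow us to detect correlation coefficients of 0.31 or larger with at least 80% power". Neither limits the statement to baseline. The same power paragraph sets out the attrition: "Assuming a conservative 12.5% loss-to-follow-up at 6 months (35 participants/group remaining").

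The exploratory list asks: "Do NAE and calcium excretion correlate at baseline and other time points, when controlled for kidney function and calcium intake"? Two control variables are named, and arm is not one of them. The Human Subjects section says of oral bicarbonate that "this will result in decreased acid excretion by the kidney".

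**The concern.** There are two separate gaps.

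First, a single power figure is offered for all the correlational work. A correlation that uses change in NAE to 6 months can include only people measured at 6 months, and by the plan's own attrition that is fewer than 80. The figure is then slightly too favourable for those analyses.

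Second, if bicarbonate lowers NAE, change in NAE is partly a marker of which arm a person was in. A coefficient pooled over arms then has two sources: people in the same arm who differ in NAE change, and the difference between the arms. If treatment also shifts the other measure, the pooled coefficient can be non-zero with no association inside either arm. If treatment does not shift it, a real within-arm association is diluted. A confidence interval around the pooled value carries the same mixture, so the plan's emphasis on intervals does not remove the problem. What is at stake is how a reported r is interpreted, not the primary result.

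**Working it through.** **1. The plan's own figure.** Inputs from the power statements: r = 0.31, two-sided α = 0.05, n = 83 or 80. Fisher z approximation: power = Φ(atanh(r)·√(n − 3) − 1.960), with atanh(0.31) = 0.3205.

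- n = 83: 0.3205 × √80 = 2.867; power 81.8%.
- n = 80: 0.3205 × √77 = 2.813; power 80.3%.

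The required n is 3 + ((1.960 + 0.842)/0.3205)² = 79.4, so 80. The stated figure reproduces at the full randomised number.

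**2. The number left at 6 months.** 80 × 0.875 = 70, which is the plan's 35 per group. If 83 are randomised, 83 × 0.875 = 72.6, so 72 or 73. The detectable r at 80% power is tanh((1.960 + 0.842)/√(n − 3)).

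| n | Power at r = 0.31 | Detectable r |
|---|---|---|
| 83 | 81.8% | 0.303 |
| 80 | 80.3% | 0.309 |
| 73 | 76.5% | 0.323 |
| 72 | 75.9% | 0.325 |
| 70 | 74.7% | 0.330 |

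An exact bivariate-normal calculation gives 75.3% at n = 70. No two-sided variant tried reached 80% there (range 72% to 77%; the low end is Spearman with an assumed variance factor of 1.06).

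**3. The effect of pooling over arms.** The documents do not give all the inputs, so this is an illustration. Assumptions:

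- Equal arms of 35.
- The 16.5 mEq/g in the power paragraph, printed as a change, is read as the within-arm SD of change. In support, 11.4 / (√(2/35) × (1.960 + 0.842)) = 17.0, close to 16.5.
- The expected change of 20-30, printed in meq/d, is read as a between-arm difference in mEq/g. The plan's detectable difference of 11.4 mEq/g is shown beside it.
- The shift in the other measure, d₂ (in SD), is assumed. No value is in the documents.

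With d₁ = NAE difference / 16.5 and ρ the within-arm correlation, and treatment lowering NAE and raising the other measure:

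pooled r = (ρ − d₁d₂/4) / √[(1 + d₁²/4)(1 + d₂²/4)]

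share of variance in NAE change due to arm = (d₁²/4) / (1 + d₁²/4)

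| NAE difference | d₁ | Arm share | Size of pooled r, ρ = 0, d₂ = 0.5 | Size of pooled r, ρ = 0, d₂ = 0.2 | Pooled r, ρ = 0.31, d₂ = 0 |
|---|---|---|---|---|---|
| 11.4 | 0.69 | 11% | 0.08 | 0.03 | 0.29 |
| 20 | 1.21 | 27% | 0.13 | 0.05 | 0.27 |
| 25 | 1.52 | 36-37% | 0.15 | 0.06 | 0.25 |
| 30 | 1.82 | 45% | 0.16 | 0.07 | 0.23 |

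Worked line for 20: d₁ = 20/16.5 = 1.212 and 1 + d₁²/4 = 1.367. With ρ = 0 and d₂ = 0.5, the size is (1.212 × 0.5/4) / √(1.367 × 1.0625) = 0.126. With ρ = 0.31 and d₂ = 0, it is 0.31/√1.367 = 0.265.

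**4. The price of adjusting.** A partial correlation given arm uses √(70 − 3 − 1) = √66. The detectable r is tanh(2.802/√66) = 0.332, against 0.330 unadjusted. The two are different parameters, so this compares precision only.

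**The case against.** **Power.** Each power sentence is true at the number it prints, and neither mentions 6-month change. The NEAP correlations named first can use everyone at baseline. The plan calls its 12.5% loss conservative, concedes low power, and puts the emphasis on intervals. At r = 0.31 the 95% interval is 0.10 to 0.50 at n = 80 and 0.08 to 0.51 at n = 70, so no decision turns on it. All of this stands. It makes the point small but does not remove it: the statement is unqualified, change correlations are among the planned analyses, and two sample sizes are printed.

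**Arm.** The study asks whether lowering acid load helps, so variation in NAE produced by randomisation may be the signal of interest. The arm-adjusted value uses only non-randomised variation (diet, kidney function, adherence) and can be confounded. This also stands, and it is why the pooled value should be kept. A reader might infer that pooled correlations are spurious or invalid. The documents do not support that: the pooled value answers a different question, and the sizes above depend on assumed inputs.

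**Time point.** A reader might also infer that the visit for change is left open and that schedule conflicts make it unresolvable. Aim 2 could name the visit, but 6 months is the natural reading, since the Aim 1 contrast and both power paragraphs are for 6 months. The text has "electrolytes, blood glucose and creatinine will be assessed at baseline and at 6-month follow-up" where the table adds a 3-month sample, and text and table differ on 3-month blood gas and cystatin C. On any of these readings, change from the pre-treatment value to 6 months can still be computed. These differences are not part of this point.

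**Conclusion.** The point holds as a minor one, optional for the sponsor to act on.

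The power part needs only the plan's own r, α, sample sizes and loss rate. At least 80% power at r = 0.31 is right for baseline correlations. It is not delivered for 6-month change, where power is about 75% (about 76% if 83 are randomised) and the detectable r is 0.32-0.33. It would be too strong to call the plan's calculation wrong; it is correct for the numbers it states.

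The arm part is certain in kind but not in size. With no arm term and a treatment expected to lower NAE, a pooled change correlation mixes two associations. Under the stated assumptions, at NAE differences of 20-30, a 0.5 SD outcome shift alone gives a pooled r of size 0.13-0.16, and a within-arm r of 0.31 with no outcome shift falls to 0.23-0.27. At 11.4 mEq/g the figures are 0.08 and 0.29, which is little. The correlations are exploratory, and the primary comparison does not depend on them.

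**What to change.** - In both power statements, give the detectable correlation as about 0.31 for baseline analyses and about 0.33 for 6-month change, and use one sample size in both places.
- For every correlation that uses 6-month change or post-baseline values, including the post-baseline part of the NAE-calcium question, report the arm-adjusted partial Pearson and Spearman correlation with a confidence interval beside the pooled value.
- Add a sentence saying that the two answer different questions, and that the arm-adjusted value rests on non-randomised variation in NAE and can be confounded.

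The cost is SAP wording and one degree of freedom, with a slightly less favourable detectable correlation on paper. No visit, participant or measurement is added. Separate within-arm coefficients, if shown, would be descriptive only: at n = 35 the detectable r is tanh(2.802/√32) = 0.46.

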The study will be conducted at the academic medical center, specifically the Clinical Research Unit (CRU) of the Wake Forest School of Medicine (WFSM) and with the support of the Pepper Center and Translational Science Institute. The participants will be recruited from the general community and evaluated and followed by the CRU.

Subjects selection criteria

Elderly at risk for disability with mild impairment of kidney function will be selected for this study.

Inclusion Criteria	Exclusion Criteria
Age 65+ years of age	Uncontrolled (>160 mg/dl fasting blood glucose), insulin-dependent diabetes and/or uncontrolled hypertension (SBP >160 , DBP >100)
SPPB (short physical performance battery) score >3	a current diagnosis of psychotic disorder or taking anti-psychotic medication
eGFR stage 2 (60-89) or 3 (30-59)	take more than 14 alcoholic drinks per week
	plan to relocate out of the study area within the 8 months
Net endogenous acid production (NEAP) >40 mEq/d	self-reported inability to walk across a room
Willing to provide informed consent and agrees to randomization	those who reside in nursing homes
Not involved in another intervention study	have difficulty communicating with study personnel due to speech or language or hearing problems
	had cancer requiring treatment in the past 1 year
	lung disease requiring regular use of corticosteroids at a dose of >7.5 mg/d for the last 3 months or use of supplemental oxygen
	cardiovascular disease (Class III or IV congestive heart failure)
	significant valvular disease, uncontrolled angina
	myocardial infarction, major heart surgery (i.e., valve replacement or bypass surgery) in past 6 months
	stroke, deep vein thrombosis, or pulmonary embolus in the past 6 months,
	Parkinson's disease or other progressive neurological disorder
	other medical or behavioral factors that in the judgment of the principal investigator may interfere with study participation or the ability to follow the intervention
	clinical judgment concerning safety or noncompliance
	Individuals with BMI <18.5 ; or unintentional weight loss $>4\%$ in last 6 months
	MoCA score under 24
	End Stage Renal Disease (ESRD) on dialysis or primary kidney disease
	Other illness of such severity that life expectancy is less than 12 months
	Any tobacco or nicotine product use in the past year
	Serum HCO ₃ >30 meq/L; serum K ⁺ out of normal range <3.5 or >5.2

Sample Size

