An 4-hour urine collections were chosen because they can be done during the day in the Clinical Research Unit (CRU). Participants will empty their bladders before beginning the timed collection; then all urine collected over 4hrs will be pooled into a collection container. The specimen will be refrigerated during the collection period and subsequently frozen until analysis. While total urinary nitrogen and Ca⁺² will be done by LabCorp, a trained technician in our Geriatrics laboratory will determine NEA/Cr (urine ammonium + titratable acidity) using standard methods (16).

For blood gas measurements, a blood sample will be obtained from a cannulated hand vein warmed for 10-15 min at 55°C before sampling. Samples will be analyzed immediately after phlebotomy(17), using an ABL5 blood gas analyzer to measure blood pH and pCO₂; based on these measurements, the analyzer calculates serum bicarbonate using Henderson-Hasselbalch equation.

Kidney function will be determined using uACR and eGFRcys. (estimated with CKD Epidemiology Collaboration equation (CKD-EPI) (18), based on serum cystatin c levels, which will be measured by a particle-enhanced immunonephelometric assay86). The Nutrition Data System for Research (NDSR) will be used to conduct 24-hour food recalls. NDSR is a computer-based software application which will be used to assess daily protein and K+ intake needed for calculation of NEAP = [54.5x(prot (g/d) / pot (meq/d)] – 10.2, where

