Metabolomics. Metabolomics analysis of the urine samples collected at baseline and the last follow up visit will extend our preliminary findings: 1) to elderly individuals; 2) will test the predictive value of identified metabolites with targeted metabolomics and 3) will repeat the broad spectrum analysis in samples taken before and after the intervention, circumventing the uncertainty of the preliminary data, which relied on statistical associations. All analyses will be overseen by the Wake Forest School of Medicine Proteomics and Metabolomics Core (see the letter from the Director, [name]); the metabolomics samples are processed in collaboration with NIH Eastern Metabolomics Core at RTI170-74. We will use targeted metabolomics and broad spectrum ¹H NMR spectroscopy.

The copy of **the questionnaire** that will be used during the **initial phone call** to determine initial eligibility (e.g. to exclude individuals with already high consumption of fruits and vegetables (base-forming foods) or those meeting exclusion criteria based on medical history (self-reported insulin-dependent diabetes, advanced heart disease, end stage renal disease) are included in the protocol application. The **questionnaires** that will be used during **follow up telephone call and follow up visits** to evaluate safety and adherence and to collect 24hr-food recall data are also included.

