Participants will be required to attend a Screening Visit (SV) after they qualify based on the phone screener. During the screening visit they will be explained the Informed Consent and must sign to agree to participate. They will complete a Short Physical Performance Battery (SPPB) and a MoCA (Montreal Cognitive Assessment) and scores from these tests will determine initial eligibility. Study Coordinators will then ask questions regarding medical history and medications, and a Comprehensive Metabolic Panel (CMP) and urinalysis will be completed. If participants prove to be eligible based on their scores and blood work, they will be asked to come back for their Baseline Visit (BV). Usual dietary intake will also be assessed via a food frequency questionnaire at the BV1, and FV3 visits. We plan to use the VioFFQTM (Viocare, Inc., Princeton, NJ), which is a validated, web-format system for collecting food frequency data. VioFFQ collects data on a subject's dietary behavior and food use patterns, provides estimates of macronutrients, micronutrients, and servings of particular foods of interest, and delivers detailed dietary analysis data and reports. Dietary intake will also be assessed by 24-hour diet recalls. Data will be collected and analyzed using the NDSR software developed and supported by the Nutrition Coordinating Center (NCC) of the University of Minnesota. NDSR allows use of the multiple pass approach, providing interview prompts to guide and standardize data entry. Subjects will be screened to assure that they are accessible by telephone for the

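### Recall NEAP and FFQ NEAP are to be compared by correlation alone, which cannot show a systematic difference, and the baseline coefficient is further lowered because participants were selected on the same recalls

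*Combined protocol and SAP*

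**What the plan says.** Under Other Exploratory/Sensitivity Analyses the plan asks "Does NEAP calculated from food recalls correlate with NEAP calculated from FFQs". It names no visit, no set of recalls and no statistic beyond correlation. For the other NEAP associations the Analytical Plan (Aim 2) states "Correlations coefficients (both Pearson and Spearman) will be used to investigate the association". No mean difference, limits of agreement, concordance coefficient or cross-classification appears in the document.

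The entry criteria require "Net endogenous acid production (NEAP) >40 mEq/d". The section on clinical assessments says that the recall software supplies "daily protein and K+ intake needed for calculation of NEAP". For eligibility, the in-person screening recall is combined with a telephone recall made within a week of the screening visit: "an average of both protein intake and K+ will be used to calculate the NEAP score". The telephone screen also serves "to exclude individuals with already high consumption of fruits and vegetables (base-forming foods").

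On timing, the plan states "Usual dietary intake will also be assessed via a food frequency questionnaire at the BV1, and FV3 visits". The schedule table likewise ticks the FFQ at baseline and FV3 only, and ticks the 24-hour recall at screening, FV1, FV2 and FV3 but not at baseline. Later recalls fall "within a 1-week period of each follow-up visit for a total of eight recalls during the study".

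**The concern.** Recall and FFQ are two ways of estimating one quantity in mEq/d, so some correlation is expected in advance. The more informative question is whether they give the same value, and a correlation cannot answer it. The FFQ could read well below the recall in everyone and r would not move.

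The baseline coefficient has a second difficulty. It would pair the baseline FFQ with the recalls on which participants were selected. Cutting off the lower part of one variable lowers its correlation with the other, so the result would understate how closely the instruments track each other among the people who were screened.

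What is at stake is how one exploratory result is read. A high r could hide a shift, and a modest baseline r could make the FFQ look poorer than it is.

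**Working it through.** **1. The plan's own correlation figure.** Sample Size (n = 83) and the power paragraph of the Analytical Plan (n = 80) both give 0.31 as detectable with at least 80% power, two-sided 0.05. By Fisher's z, detectable r = tanh[(1.960 + 0.842)/√(n − 3)].

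- n = 80: tanh(2.802/√77) = 0.309
- n = 83: tanh(2.802/√80) = 0.303
- n = 70 (35 per group at 6 months): tanh(2.802/√67) = 0.330

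The stated figure is reproduced for 80 and for 83. It refers to the coefficient in the enrolled sample.

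**2. Blindness to shift and scale.** For b > 0, corr(X, a + bY) = corr(X, Y). In a simulated sample of 80 pairs, replacing one method's value Y by 0.6Y − 5 left r at 0.807.

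To put this in mEq/d, assume bivariate normal NEAP with mean 50, SD 15 and unselected r 0.6 (none of these is in the documents), selected on recall > 40:

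| Constant FFQ bias (mEq/d) | r among enrolled | FFQ at or below 40 |
|---|---|---|
| 0 | 0.48 | 16% |
| −10 | 0.48 | 39% |
| +10 | 0.48 | 4% |

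**3. Attenuation at baseline.** Let q be the share removed by the cut, a = Φ⁻¹(q), λ = φ(a)/(1 − q) and u² = 1 + aλ − λ². Then r in the selected sample = r·u/√(1 − r² + r²u²). The documents give neither q nor r, so a range is shown:

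| Share screened out | u | r = 0.30 | r = 0.50 | r = 0.70 |
|---|---|---|---|---|
| 10% | 0.844 | 0.26 | 0.44 | 0.64 |
| 25% | 0.731 | 0.22 | 0.39 | 0.58 |
| 50% | 0.603 | 0.19 | 0.33 | 0.51 |
| 75% | 0.492 | 0.15 | 0.27 | 0.43 |

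Example for r = 0.50 and q = 50%: 0.50 × 0.603/√(0.75 + 0.25 × 0.363) = 0.33. Skewed (lognormal) NEAP gave the same direction in every scenario tried, for Pearson and for Spearman.

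A later recall, not itself used for selection, is attenuated less. With half screened out and an assumed reliability of 0.5 for both instruments, r goes from 0.50 to 0.41, against 0.33 for the screening recall.

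**4. Why agreement should not use the screening recalls.** With no true bias and equal means and SDs, the expected recall-minus-FFQ difference among those selected is (1 − r) × SD × λ. For mean 50, SD 15 and cut 40:

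- a = −0.667, q = 0.252, λ = 0.427
- r = 0.6: 0.4 × 15 × 0.427 = 2.56 mEq/d (recall mean 56.4, FFQ mean 53.8)
- r = 0.3: 0.7 × 15 × 0.427 = 4.5 mEq/d

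This is pure regression to the mean. In the simulation with later recalls, whose errors were independent of the screening errors, the difference was about 0.

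**5. Precision at 6 months.** In units of the SD of the differences, with n = 70:

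- mean difference, 95% CI half-width: 1.96/√70 = 0.23
- each limit of agreement: 1.96 × √(1/70 + 1.96²/(2 × 69)) = 0.40

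**The case against.** The plan asks whether the two measures correlate, and a correlation answers that. NEAP's stated analytical role is as a correlate of other measures; for that, similar ranking of participants is what counts and a constant shift does no harm. The comparison is one exploratory line in a feasibility pilot and is not among the aims or outcome measures. All of this stands and keeps the point small.

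A reader might infer that the FFQ is meant to replace recalls for screening, so that the coefficient would steer a future trial's entry rule. The documents do not support this. Eligibility rests on recalls, the FFQ is given after eligibility is settled, and no section proposes it for screening. That use is hypothetical.

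A reader might also infer that the baseline coefficient is simply wrong. It is low only relative to the unselected screened population. For enrolled participants, in whom every other NEAP correlation is run, the restricted coefficient is the relevant one. The plan does not claim to estimate the unselected one, and its 0.31 is correctly calculated.

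What remains is that no planned statistic would reveal a systematic difference between the instruments, and that nothing warns the reader about selection at baseline.

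**Conclusion.** The point holds as a modest improvement. Correlation is the only planned comparison, and it cannot show whether recall NEAP and FFQ NEAP differ systematically. That follows from the definition and needs no assumption.

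The direction of the baseline attenuation is well supported, because selection is on the same recalls. Its size is not fixed by the documents, which give no NEAP distribution, screen-out share or expected correlation. An unselected r of 0.50 could become anything from about 0.44 to 0.27 over screen-out shares of 10% to 75%. No single value from the tables should be read as this trial's attenuation.

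It would be tempting to ask for agreement statistics at baseline as well. The schedule does not support that: no recall is set for the baseline visit, so the analysis would reuse the selection recalls and show a difference of about 2.6 mEq/d with no true bias, under mean 50, SD 15 and r 0.6. A same-side-of-40 percentage there would also be one-sided, since every enrolled participant has a screening recall NEAP above 40.

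The primary NAE/Cr analysis and its sample size do not depend on any of this.

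**What to change.** In Other Exploratory/Sensitivity Analyses, specify the following for the 6-month visit (FV3 in the schedule table), where recall and FFQ are both scheduled and the recalls were not used for selection:

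- the mean recall-minus-FFQ difference in NEAP with its 95% CI;
- Bland-Altman 95% limits of agreement;
- the percentage of participants whom both instruments place on the same side of 40 mEq/d, as a description of the enrolled group only.

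State which recalls make up the FV3 value. Keep the correlation as descriptive, and label any baseline coefficient as restricted to participants selected on recall NEAP above 40. Do not run the agreement analysis on the screening recalls.

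The cost is a few lines of analysis on data already scheduled, with no added visit or procedure. The limits are that only about 70 pairs are expected at 6 months (CI half-width about 0.23 SD of the differences for the mean difference and 0.40 SD for each limit), and that the results describe people selected for high NEAP, not everyone screened.
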